5.3.4 Biomarkers

Nectin-4 expression in tissue will be assessed by IHC H-score.

PD-L1 expression in tissue will be assessed by IHC combined positive score (CPS) for HR+/HER2- breast cancer (Cohort 1), TNBC (Cohort 2), head and neck cancer (Cohort 5), gastric adenocarcinoma or esophageal adenocarcinoma or GEJ adenocarcinoma (Cohort 7), esophageal squamous cell carcinoma (ESCC) (Cohort 8) and first-line head and neck squamous cell carcinoma (Cohort 9). PD-L1 expression in tissue will be assessed by IHC Tumor Proportion Score (TPS) for squamous or non-squamous non-small cell lung cancer (Cohorts 3 and 4).

Additional biomarkers may be evaluated to explore effects on anti-tumor activity and safety of the study drug and will be described in a separate biomarker analysis plan.

5.3.5 Pharmacokinetic Endpoints

To assess the pharmacokinetics of enfortumab vedotin and monomethyl auristatin E (MMAE), the following pharmacokinetic endpoints will be evaluated:

- Plasma concentration of MMAE
- Serum concentration of enfortumab vedotin

5.3.6 Incidence of Antitherapeutic Antibodies

The incidence of ATA formation to the enfortumab vedotin will be evaluated.

5.3.7 Patient Reported Outcome

5.3.7.1 Cohorts 1 to 8

To evaluate the treatment effect of enfortumab vedotin on quality of life, PRO per Euro quality of life - 5 dimensions (EQ-5D-5L) and global pain assessment (worst pain in the last 24 hours) will be assessed.

- EQ-5D-5L

The EQ-5D-5L is a standardized instrument developed by the EuroQOL Group for use as a generic, preference-based measure of health outcomes. It is applicable to a wide range of health conditions and treatments and provides a simple descriptive profile and a single index value for health status. The EQ-5D-5L is a 5-item self-reported measure of functioning and well-being, which assesses 5 dimensions of health, including mobility, selfcare, usual activities, pain/discomfort, and anxiety/depression. Each dimension comprises 5 levels (no problems, slight problems, moderate problems, severe problems, extreme problems). This questionnaire also records the respondent's self-rated health status on a vertical graduated (0 to 100) visual analogue scale (VAS) [Herdman, 2011].

A unique EQ-5D-5L health state is defined by combining 1 level from each of the 5 dimensions: this defines a profile that is primarily reported as 5-digit number, for instance 11221. A total of 3125 possible health states are defined in this way. For example, state 11111 indicates no problems on any of the 5 dimensions, while 12345 indicates no problems with mobility, slight problems with washing or dressing, moderate problems with doing usual activities, severe pain or discomfort and extreme anxiety or depression. The instrument was specifically designed to provide an overall single number, called weighted index or utility index, for each of the health states resulting from the combination of item response [Dolan, 1997]. The utility index can be only derived from patients who have provided a complete 5-response profile. A higher index indicates better QoL. The EQ-5D-5L utility index value will be derived using the value set for England [Devlin, 2012]. The algorithm to calculate the utility index using England value set is presented in Appendix 9.3.

The analysis population is FAS.

- Global pain assessment

Global pain assessment is a subject's rating of his/her pain on a 0 to 10 scale that best describes the pain at its worst in the last 24 hours. Refer to Protocol Appendix 12.11 for a sample questionnaire.

The analysis population is FAS.

PRO completion status at each visit will be reported for each instrument:

- Completion rate at each visit will be calculated as the number of subjects with at least one question completed divided by the number of subjects in the FAS population
- Compliance rate at each visit will be calculated for subjects who are expected to have PRO assessment at the visit. The following will be provided:
 - The number and percentage of subjects with at least one questions completed
 - The number and percentage of subjects with all questions completed (for EQ-5D-5L only)
 - The number and percentage of subjects with either utility index calculated or VAS completed (for EQ-5D-5L only)

5.3.7.2 Cohort 9

- EORTC QLQ H&N43

The EORTC QLQ H&N43 contains 43 items of 12 multi-item and 7 single-item symptom subscales namely pain in the mouth, swallowing, problems with teeth, dry mouth and sticky saliva, problems with senses, speech, body image, social eating, sexuality, problems with shoulder, skin problems, fear of progression, problems opening mouth, coughing, social contact, swelling in the neck, weight loss, problems with wound healing, neurological problems. Patients report the extent to which they have experienced these symptoms or problems during the past week. The scores are

from 1 to 4 (0 - not at all; 1 - A little; 2 - Quite a bit; 4 - very much). Refer to Protocol Appendix 12.13 for a sample questionnaire. The analysis population is FAS.

- Global Pain Assessment

Global pain assessment is a subject's rating of his/her pain on a 0 to 10 scale that best describes the pain at its worst in the last 24 hours. Refer to Protocol Appendix 12.11 for a sample questionnaire. The analysis population is FAS.

- PRO-CTCAE

Three questions will be utilized from the PRO-CTCAE to obtain subject assessment of fatigue and diarrhea symptoms. Patients report the frequency, severity and interference of the symptoms in the past 7 days. The diarrhea frequency question comprises 5 levels from Never to Almost constantly. The fatigue severity question comprises 5 levels from None to Very severe. The fatigue interference question comprises 5 levels from Not at all to Very much. Refer to Protocol Appendix 12.14 for a sample questionnaire. The analysis population is FAS.

- FACT-G

Functional Assessment of Cancer Therapy – General (FACT-G) Version 4 is a 27 item questionnaire designed to measure four domains of HRQOL in cancer patients: Physical, social, emotional, and functional well-being. Original development and validation involved 854 patients with cancer and 15 oncology specialists. Subjects with cancer aged 18 years and older are asked to recall the past 7 days and complete the questionnaire. EV-202 cohort 9 will include a single question from the “Physical Well-Being” domain, GP5 “I am bothered by side effects of treatment” which is self-scored from “0 to 4” (0 - not at all; 1 - A little bit; 2 - Somewhat; 3 - Quite a bit; 4 - very much). Refer to Protocol Appendix 12.15 for a sample questionnaire. The analysis population is FAS.

PRO completion status at each visit will be reported for each instrument:

- Completion rate at each visit will be calculated as the number of subjects with at least one question completed divided by the number of subjects in the FAS population
- Compliance rate at each visit will be calculated for subjects who are expected to have PRO assessment at the visit. The following will be provided:
 - The number and percentage of subjects with at least one questions completed
 - The number and percentage of subjects with all questions completed (for EORTC QLQ H&N43 and PRO-CTCAE only)

5.4 Safety Endpoints

Safety endpoints including adverse events (AEs), laboratory test, vital signs, 12-lead electrocardiogram (ECGs) and Eastern Cooperative Oncology Group (ECOG) performance status are secondary endpoints of the study.

Safety will be assessed by evaluation of the following variables:

- Treatment-emergent adverse events (TEAEs; frequency, severity, seriousness, and relationship to study drug).
 - TEAE is defined as an adverse event observed after starting administration of the study drug and within 30 days after taking the last dose of study drug. For serious AEs in Cohort 9, TEAE definition is revised to within 90 days after the last dose of either study drug. If the adverse event occurs on the first dose date and the onset check box is marked “Onset after first study drug taken” or the onset check box is left blank, then the adverse event will be considered treatment emergent. If the adverse event occurs on the first dose date and the onset check box is marked “Onset before first study drug taken”, then the adverse event will not be considered treatment emergent. If a subject experiences an event both during the pre-investigational period and during the investigational period, the event will be considered as TEAE only if it has worsened in severity (i.e., it is reported with a new start date). If a complete onset date is unknown, and the onset check box is marked “Onset after first study drug taken”, then the adverse events will be considered treatment emergent. If the onset check box is marked “Onset before study drug taken”, then the adverse event will not be considered treatment emergent. If onset check box is left blank, imputed onset date as specified in Section 6.9.2 will be used to determine whether an adverse event is treatment emergent.
 - A drug-related TEAE is defined as any TEAE with relationship to study drug (enfortumab vedotin or pembrolizumab) marked as “Yes” on eCRF as assessed by investigators or with missing assessment of the causal relationship.
- Serious adverse events (SAEs) include adverse events that are flagged as serious by the investigator on eCRF, or with missing serious assessment on eCRF, or upgraded by the Sponsor based on review of the Sponsor’s list of Always Serious term or the important medical event process.
- Adverse events of special interest for enfortumab vedotin (AESI)
 - For cohorts 1 to 9, hyperglycemia, peripheral neuropathy, dry eye, corneal disorders and blurred vision, skin reactions, and infusion related reactions are considered adverse events of special interest (AESI) for enfortumab vedotin. These are medical concepts of composite terms based on the search criteria utilizing MedDRA terminology (standard MedDRA query [SMQ], sponsor specific query [SSQ], customized MedDRA query [CMQ], high level group term [HLGT], high level term [HLT], preferred term [PT]). Other AEs may be added as AESI as necessary due to ongoing pharmacovigilance activities. The search criteria for AESI will be maintained in a separate document and finalized prior to database lock.
 - For selected AESI, time to onset of AESI will be calculated. Time to first onset of a specific AESI will be calculated as the time from the first dose of study drug to the onset of the first treatment-emergent adverse event that meets the respective search criteria.

- For selected AESI, time to resolution of AESI will be calculated. Resolution is defined as event outcome of ‘recovered/resolved’ or ‘recovered/resolved with sequelae’. For treatment-emergent events with an outcome of ‘recovered/resolved’ or ‘recovered/resolved with sequelae’, time to resolution will be calculated as time from the event onset date to end date.

Time to resolution is defined at the event level. AE records that belong to the same event will be linked.

- Other AEs of risk for enfortumab vedotin
For cohorts 1 to 9, pneumonitis/interstitial lung disease (ILD) is defined as other AEs of risk for EV. Similar as AESI, terms are based on the search criteria utilizing MedDRA terminology.
- Adverse events of special interest for pembrolizumab (AEOSI)
 - For cohort 9, AEOSI are immune-mediated events and infusion-related reactions, following the Keytruda AEOSI List which is a pre-specified list of preferred terms (PTs) developed by MSD to consistently characterize the nature and frequency of each AEOSI across the clinical program, regardless of causality as reported by investigators. These PTs are considered to be medically equivalent to the identified risks for pembrolizumab. The list of PTs may be updated by MSD based on emerging pembrolizumab safety data or as a result of MedDRA updates.
- Clinical laboratory variables

Below is a table of the laboratory tests that will be performed during the conduct of the study.

Panel/Assessments	Parameters to be Analyzed	NCI-CTCAE Grading (Hyper/Hypo)
Hematology	Hematocrit (Hct) Hemoglobin (Hb) Platelets Red blood cell count (RBC) White blood cell count (WBC) White blood cell count differential 
 Absolute neutrophils count (ANC) Eosinophils Basophils Lymphocytes Monocytes 	N/A Both Hypo N/A Both Hypo N/A N/A Both N/A
Biochemistry	Albumin (Alb) Alanine aminotransferase (ALT) Alkaline phosphatase (ALP) Aspartate aminotransferase (AST) Bicarbonate (HCO ₃) Bilirubin (total and direct) Blood urea nitrogen (BUN) Calcium corrected (CCa) Chloride (Cl) Creatinine Glucose Hemoglobin A1c (HbA1c, screening and EOT only) Lactate dehydrogenase (LDH) Magnesium (Mg) Phosphate (P) Potassium (K) Sodium (Na) Total protein (TP) Uric Acid Lipid panel (screening only), including: 
 Total cholesterol (T chol) High-density lipoprotein cholesterol (HDL-C) Low-density lipoprotein cholesterol (LDL-C) Triglycerides (Trig) 	Hypo Hyper Hyper Hyper N/A Hyper N/A Both N/A Hyper Both Both Both Both N/A Hyper Hyper N/A N/A Hyper
Thyroid Function Tests (Cohort 9 only)	Triiodothyronine (T3) or Free Triiodothyronine (FT3) Free thyroxine (FT4) Thyroid stimulating hormone (TSH)	N/A N/A N/A
Coagulation (Cohort 9 only)	INR PT PTT	Hyper N/A Hyper
Pregnancy Test	Serum or urine β -human Chorionic Gonadotropin (hCG).	N/A

- Vital signs (systolic and diastolic blood pressure (mmHg), pulse rate (beats/minute), and body temperature (°C))
- 12-lead electrocardiogram (ECG)
- ECOG performance scores

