7.3.1 Time Period for Collecting Adverse Event and Serious Adverse Event Information

In order to identify any events that may be associated with study procedures and could lead to a change in the conduct of the study, Astellas collects AEs even if the subject has not received investigational product. AE and ECI collection begins after the signing of the ICF and will be collected until 30 days after the last dose of investigational product administration or when the subject is determined to be a screen failure. SAEs related to pembrolizumab will be collected until 90 days after following cessation of study treatment, or 30 days following cessation of study treatment if the subject initiates new anticancer therapy, whichever is earlier.

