7.3.4 Reporting of Serious Adverse Events

Prompt notification by the investigator to the sponsor of an SAE is essential, so that legal obligations and ethical responsibilities towards the safety of subjects and the safety of a study intervention under clinical investigation are met.

In the case of an SAE, the investigator must contact the sponsor by fax or email immediately (within 24 hours of awareness).

Procedures for reporting SAEs to the sponsor are described in [Section 12.4.5 Reporting Procedures for Serious Adverse Events].

7.3.5 Disease-related Events and/or Disease-related Outcomes Not Qualifying as Adverse Events or Serious Adverse Events

Under this protocol, the following event(s) will not be considered as an (S)AE:

- Disease progression: events including defined study endpoints that are clearly consistent with the expected pattern of progression of the underlying disease are not to be recorded as AEs. These data will be captured as efficacy assessment data as outlined in [Section 7.1 Efficacy Assessments]. If there is any uncertainty as to whether an event is due to anticipated disease progression and/or if there is evidence suggesting a causal relationship between the investigational product and the event, it should be reported as an (S)AE. All deaths up to 30 days after the final administration of investigational product must be reported as an SAE, even if attributed to disease progression. For subjects in Cohort 9 receiving pembrolizumab, all deaths up to 90 days after the final administration of pembrolizumab must be reported as an SAE, even if attributed to disease progression.
- Pre-planned and elective hospital/clinical procedures/interventions or procedures for diagnostic, therapeutic, or surgical procedures for a preexisting condition that did not worsen during the course of the study. These procedures are collected per the eCRF's completion guidelines.

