9.5 Analysis of Safety

9.5.1 Adverse Events

AEs will be coded using the Medical Dictionary for Regulatory Activities (MedDRA).

A TEAE is defined as an AE observed after starting administration of study drug and within 30 days after the final administration of study drug. A drug-related TEAE is defined as any TEAE with a causal relationship assessed as “yes” by the investigator.

The number and percentage of subjects with TEAEs, drug-related TEAEs, serious TEAEs, drug-related serious TEAEs, TEAEs leading to withdrawal of treatment and drug-related TEAEs leading to withdrawal of treatment will be summarized by system organ class (SOC), preferred term, cohort, and overall. The number and percentage of TEAEs by severity will also be summarized. The worst severity will be summarized if the same AE is recorded more than once for a subject.

AE data will be listed.

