6.5 Analysis of Safety

All analysis of safety will be presented by cohort and overall for the SAF, unless specified otherwise.

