6.5.1 Adverse Events

All adverse events recorded on treatment including within 30 days from the last study treatment, or within 90 days from the last study treatment for SAEs in Cohort 9 will be summarized.

Summaries and listings of SAEs include SAEs upgraded by the sponsor based on review of the Sponsor's list of Always Serious terms or the important medical event process if any upgrade was done.

The coding dictionary for this study will be MedDRA. It will be used to summarize AEs by SOC and PT. AEs will be graded using National Cancer Institute's Common Terminology Criteria for AEs (NCI-CTCAE).

The definition of TEAEs leading to treatment discontinuation, TEAEs leading to interruption of treatment and TEAEs leading to dose reduction is listed below. The rules will be followed in the applicable TEAE analyses.

- TEAEs leading to permanent discontinuation of study drug is defined as TEAEs leading to withdrawal of any study drug (enfortumab vedotin or pembrolizumab) in Cohorts 1-9. TEAEs leading to permanent discontinuation of enfortumab vedotin is defined as TEAEs leading to withdrawal of enfortumab vedotin in Cohort 9. TEAEs

leading to permanent discontinuation of pembrolizumab is defined as TEAEs leading to withdrawal of pembrolizumab in Cohort 9.

- TEAEs leading to dose interruption is defined as TEAEs leading to interruption of any study drug (enfortumab vedotin or pembrolizumab) in Cohorts 1-9. TEAEs leading to interruption of enfortumab vedotin is defined as TEAEs leading to interruption of enfortumab vedotin in Cohort 9. TEAEs leading to interruption of pembrolizumab is defined as TEAEs leading to interruption of pembrolizumab in Cohort 9.
- TEAEs leading to dose reduction is defined as TEAEs leading to reduction of enfortumab vedotin in Cohorts 1-9. Pembrolizumab reduction is not allowed.

An overview table to report the number and percentage of subjects and another overview table to report number of events and events adjusted by patient year of drug exposure will include the following details by cohort and overall:

- Number and percentage of subjects with TEAEs,
- Number and percentage of subjects with drug-related TEAEs,
- Number and percentage of subjects with serious TEAEs,
- Number and percentage of subjects with serious drug-related TEAEs,
- Number and percentage of subjects with TEAEs leading to permanent discontinuation of study drug,

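### Cohort 9 serious TEAEs are counted to 90 days for all causes, but after day 30 the protocol systematically collects only pembrolizumab-related SAEs and deaths

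*SAP*

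**What the plan says.** **SAP.** Section 5.4 defines a TEAE as an event after the start of study drug and "within 30 days after taking the last dose of study drug". It then makes one exception: "For serious AEs in Cohort 9, TEAE definition is revised to within 90 days after the last dose of either study drug". Section 6.5.1 repeats it for the tables, where events on treatment and to 30 days are included, "or within 90 days from the last study treatment for SAEs in Cohort 9 will be summarized". Neither place limits the extension by causality or ends it when new anticancer therapy starts. Section 6.5 adds: "All analysis of safety will be presented by cohort and overall for the SAF, unless specified otherwise".

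**Protocol.** Section 9.5.1 defines a TEAE as an event after the start of study drug and "within 30 days after the final administration of study drug", with no cohort 9 exception. Section 7.3.1 says that AEs "will be collected until 30 days after the last dose of investigational product administration", and that "SAEs related to pembrolizumab will be collected until 90 days after following cessation of study treatment". That extension falls back to 30 days if new anticancer therapy begins. Footnote 9 to the cohort 9 schedule (Table 2) gives the same rule. Section 7.3.5 adds, for cohort 9, that "all deaths up to 90 days after the final administration of pembrolizumab must be reported as an SAE, even if attributed to disease progression". Section 7.3.3 asks the investigator to notify the sponsor of any later event that comes to their attention and may be related to the investigational product or study participation.

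**The concern.** The SAP asks for an all-cause count over a period in which the protocol does not collect all causes. A non-fatal SAE that the investigator judges unrelated to pembrolizumab is inside the SAP's definition on day 60, but nothing requires it to be recorded. A reader of the cohort 9 serious-TEAE row would take it for a 90-day incidence, and it is not one. It is not a 30-day incidence either.

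Safety of the combination is a secondary objective of cohort 9. The natural use of these tables is to set the combination beside the monotherapy cohorts, and part of any difference would then come from the window and the collection rule rather than from the regimen.

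**Working it through.** The plan gives no figure on this point to reproduce. The check is a comparison of texts, followed by simple arithmetic on the possible size.

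**1. What days 31-90 hold in cohort 9**

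| Event on days 31-90 | In the SAP serious-TEAE count? | Collected under the protocol? |
|---|---|---|
| SAE related to pembrolizumab, no new anticancer therapy | Yes | Yes (7.3.1, Table 2 footnote 9) |
| Non-fatal SAE after new anticancer therapy starts | Yes | Not systematically |
| Non-fatal SAE not related to pembrolizumab | Yes | Not systematically; if possibly related to enfortumab vedotin, ad hoc under 7.3.3 |
| Death from any cause, progression included | Yes | Yes, to 90 days after the last pembrolizumab dose (7.3.5) |

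The numerator is thus complete to day 30 and selected by causality and by death afterwards.

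**2. Comparison with cohorts 1 to 8**

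The post-dose window is 90 days against 30, a ratio of 3 and 60 extra days. A progression death on day 60 is reportable as an SAE in cohort 9 and can enter the serious and fatal TEAE rows. The same death in cohorts 1 to 8 is outside the window. Because the 90-day clause sits in the TEAE definition itself, a late serious event also counts in the any-TEAE rows, and in the grade 3 or higher rows if graded so. Those rows then mix 90-day serious events with 30-day non-serious ones.

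**3. Anchor dates**

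Three are in use: the last dose of either drug (SAP 5.4), cessation of study treatment (Protocol 7.3.1) and the last pembrolizumab dose (Protocol 7.3.5). Protocol 8.1 lets a subject continue on enfortumab vedotin alone. Suppose, as an illustration, that enfortumab vedotin continues for 60 days after the last pembrolizumab dose. The 90-day death rule then ends 90 - 60 = 30 days after the last enfortumab vedotin dose, while the SAP window, read as running from the later drug, lasts 60 days more.

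**4. Possible size**

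Inputs: about 40 subjects in cohort 9 and about 320 in total (Protocol synopsis). The weight of cohort 9 in the overall column is 40/320 = 0.125. Let *e* be the share of cohort 9 subjects whose only serious TEAE falls on days 31-90. The documents do not give *e*, so a range is assumed.

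- Rise in the cohort 9 column = *e*
- Rise in the overall column = 0.125 x *e*

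| *e* (assumed) | Subjects of 40 | Cohort 9 rise | Overall rise |
|---|---|---|---|
| 2.5% | 1 | 2.5 points | 0.31 points |
| 5% | 2 | 5 points | 0.63 points |
| 10% | 4 | 10 points | 1.25 points |
| 20% | 8 | 20 points | 2.5 points |

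With a common 30-day window both rises are zero.

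**The case against.** The longer window is deliberate. The protocol notes that immune-mediated events can appear months after the last pembrolizumab dose, and the SAP revision log records the cohort 9 definition as an intended addition. That justifies reporting late events. It does not justify labelling them as an all-cause serious-TEAE incidence when the other causes were not collected.

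The SAP also offers fatal-TEAE rows that leave out disease progression, in the overview and in the tables by system organ class and preferred term. This helps, but only in part. Those rows do not equalise the window, they do not touch the serious-TEAE rows, and the list by preferred term alone lacks them.

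Four stronger readings are tempting and are not supported.

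- *Everything recorded after day 30 is pembrolizumab-related.* The all-deaths rule and the Protocol 7.3.3 notification rule both bring in other events.
- *The drug-related share of serious TEAEs must rise.* It can fall. As an assumed example, take 8 related among 18 cohort 9 subjects with serious TEAEs, 8/18 = 44%. Add one new subject with a related SAE and four with unrelated progression deaths: 9/23 = 39%.
- *The fraction of late SAEs missed can be read from the protocol's integrated enfortumab vedotin safety data.* Those data count subjects on monotherapy, with relatedness to enfortumab vedotin, and say nothing about days 31-90.
- *Cohort 9 should leave the overall column altogether.* That column is specified in the protocol (sections 9 and 9.5.1), and cohort 9 has its own column beside it. SAP 6.5.1 already defines the pembrolizumab discontinuation and interruption categories for cohort 9. Removing cohort 9 from overall summaries is largely a matter of preference.

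**Conclusion.** The mismatch stands and should be corrected. As written, the cohort 9 serious and fatal TEAE rows combine a complete 30-day set with a selected day 31-90 set, depart from the protocol's own TEAE definition, and cannot be compared directly with cohorts 1 to 8.

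The main harm is to the reading of the cohort 9 column and its comparison with the other cohorts. The effect on the overall column is modest: about 0.3 to 2.5 points, against 2.5 to 20 points in cohort 9. Both ranges rest on assumed late-event shares of 2.5% to 20% and on planned enrolment of 40 in 320; the true size cannot be derived from the documents. The point concerns safety reporting only and leaves the primary response analysis untouched.

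**What to change.** In SAP 5.4 and 6.5.1:

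- Use the 30-day window of Protocol 9.5.1 for all-cause serious TEAEs in cohort 9, and so in the overall column.
- Report pembrolizumab-related SAEs and deaths on days 31-90 in a separate cohort 9 table. Its title or footnote should say what was collected: related SAEs until new anticancer therapy starts, all deaths, and any ad hoc reports shown as such.
- State one anchor date for that table, and reconcile it across SAP 5.4, Protocol 7.3.1 and Protocol 7.3.5.

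The cost is edits to the SAP and table shells and one extra table, plus a protocol clarification if the agreed anchor differs from 7.3.1 or 7.3.5. No collected event is lost from the report. Changing the SAP window alone would not give a true 90-day all-cause incidence, because the protocol does not systematically collect the other events.
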